3.10.2 Off-Study Visit

Prior to removal from study, effort must be made to have all subjects complete a safety visit approximately 30 days following the last dose of study therapy.

If patient does not return for off study follow up safety visit, patient will be taken off study per appropriate reason listed in section **3.10.3**.

During the follow up safety visit, the following study tasks will be performed:

- A complete physical (including baseline blood pressure measurement) and neurological examination (include documentation of the patients' Karnofsky Performance Status).
- MD Anderson Symptom Inventory-Brain Tumor Module (MDASI-BT) (**Error! Reference source not found.**)
- Laboratory tests will include CBC, differential, platelets, total protein, albumin, calcium, phosphorus, magnesium, glucose, BUN, creatinine, sodium, potassium, total bilirubin, alkaline phosphatase, LDH, SGPT (ALT), SGOT (AST) and a pregnancy test for women of childbearing potential.
- Take patient off study (section **Error! Reference source not found.**)

3.10.3 Off-Study Criteria

- Participant requests to be withdrawn from study
- Patients lost to or refuse to follow up

- Death
- Screen failure
- PI discretion based on clinical indications
- Patient to start alternative therapy
- Patient completed follow up period
- Phase II patient completed follow up until death

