1.1.2 Secondary Objectives

1.1.2.1 To select the treatment regimen with better PFS4 between Zotiraciclib (TG02) plus dd TMZ or mn TMZ at each of the MTDs following cohort expansion.

1.1.2.2 To determine the objective response rate, PFS at 6 months (PFS6) and overall survival (OS) in the treatment arms.

1.1.2.3 To longitudinally evaluate patient reported outcome measures using self-reported symptom severity and interference with daily activities using the MDASI-BT

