3.6 ASSESSMENTS AFTER COMPLETION OF STUDY THERAPY

Follow-Up Phase – Survival/Post-Disease Progression

Once a subject completes Phase II of study therapy or starts a new anti-cancer therapy, the subject moves into the survival follow up phase and should be contacted approximately within every 6 months to assess for survival status until death, withdrawal of consent, or the end of the study, whichever occurs first.

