6.3.8 Progression-Free Survival

PFS is defined as the duration of time from start of registration to time of progression or death, whichever occurs first.

6.3.9 Time to Death:

From date of registration to date of death due to any cause.

6.3.10 Neurological Exam:

Although not used for determining response, it is useful to evaluate improvement in the neurologic exam, (as compared to the baseline assessment), that should coincide with objective measurement of tumor size. The criteria are as follows:

- 0= No neurologic symptoms, fully active at home/work without assistance
- 1= Minor neurologic symptoms, fully active at home/work without assistance
- 2= Moderate neurologic symptoms, fully active at home/work but requires assistance
- 3= Moderate neurologic symptoms, less than fully active at home/work and requires assistance
- 4= Severe neurologic symptoms, totally inactive requiring complete assistance at home or institution, unable to work

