Early stop probability	0.014	0.096	0.345	0.716	0.939
Average sample size	39.6	37.3	31.0	21.3	13.5

At progression, patients on the control arm will be offered treatment with Zotiraciclib (TG02) in combination with continued treatment with TMZ. If an effective salvage regimen, this may impact the secondary OS endpoint, but will not affect the primary endpoint of the study. The maximum number is 80 patients.

Statistical Analysis Plan

We will use descriptive statistics to summarize the demographic and clinical characteristics of patients. We will tabulate adverse events by grade by dose level and overall. For the cohort expansion and phase II component, we will estimate the proportion of patients with response with 95% exact binomial confidence intervals, and use descriptive statistics to summarize response duration. We will estimate PFS/OS with the Kaplan-Meier product limit estimator. Log-rank test will be used to compare the PFS/OS between Zotiraciclib (TG02)+TMZ and TMZ.

Changes of symptom burden (i.e., MDASI-BT) through study time points will be assessed by paired t-tests and linear mixed model. In the mixed model, subject-specific random intercept will be used to account for within-subject correlation, and measurement time will be included as a covariate. A sample size of 40 patients has 80% power to detect an effect size of 0.454 between time points using a two-tailed test with an alpha of 0.05. The two-sample t-test and linear mixed model will be used to evaluate differences in symptom burden using the MDASI-BT between Zotiraciclib (TG02) plus TMZ and TMZ. Cox proportional hazard model will be used to evaluate the relationship between MDASI-BT and disease progression. Logistic regression will be used to evaluate the relationship between MDASI-BT and tolerance to treatment.

Treatment effects will be evaluated by advanced MRI imaging study. Perfusion and diffusion – based MRI parameters, including but not restricted to blood volume, blood flow mean and median Apparent Diffusion Coefficient (ADC) value will be analysed. Results will be summarized. The mean and median value at different time points will be tabulated. Changes in such parameters will be analysed for statistical significance and correlate with the disease status.

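### The off-study list in 3.10.3 ends participation when alternative therapy starts, with no phase limit, while 3.6 sends the same patient into survival follow-up; the conflict could cost OS deaths in both arms

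*Combined protocol and SAP*

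**What the plan says.** Four provisions in the combined protocol and SAP govern what happens to survival data when a patient moves to another treatment.

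- Section 3.10.3 (Off-Study Criteria) includes the bullet "Patient to start alternative therapy". It names no phase and no arm.
- The last bullet of the same list is "Phase II patient completed follow up until death". It is the only bullet there that names a phase.
- Section 3.6 says that a subject who "starts a new anti-cancer therapy, the subject moves into the survival follow up phase" is contacted about every 6 months "to assess for survival status until death, withdrawal of consent, or the end of the study, whichever occurs first".
- Section 3.10.2 ends the list of tasks for the 30-day safety visit with "Take patient off study", and makes no exception for survival follow-up.

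OS matters to the analysis. It is a secondary objective in 1.1.2 ("To determine the objective response rate, PFS at 6 months (PFS6) and overall survival (OS) in the treatment arms"). Section 6.3.9 measures time to death as "From date of registration to date of death due to any cause". The analysis plan in section 10.2 states: "Log-rank test will be used to compare the PFS/OS between Zotiraciclib (TG02)+TMZ and TMZ". No rule says how OS is handled for a patient taken off study because of a new therapy.

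**The concern.** The same event has two incompatible consequences. A Phase II patient cannot be off study under 3.10.3 and also under survival follow-up under 3.6. Nor can a patient already off study for next-line therapy reach the last bullet of 3.10.3.

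If staff act on the alternative-therapy bullet, survival contacts stop at next-line therapy and the patient is censored there by default. Next-line therapy usually follows progression, when the risk of death is higher, so such censoring would be informative and would push the Kaplan-Meier curve upwards.

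The two arms would probably not be affected alike. Sections 3.2.2 and 10.2 offer zotiraciclib plus continued TMZ at progression to control patients only. Under 3.10.1, a control patient who crosses over leaves protocol therapy for progression only at a later progression. Combination patients have no such step, so they would tend to reach alternative therapy sooner.

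**Working it through.** **1. The texts side by side, for a Phase II patient who starts another anticancer therapy**

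| Provision | Consequence |
|---|---|
| 3.6 | Enters survival follow-up until death, withdrawal or study end |
| 3.10.3, last bullet | Leaves the study only once followed to death |
| 3.10.3, alternative-therapy bullet | Leaves the study now |
| 3.10.2, 30-day visit | Leaves the study at that visit |

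Two provisions point to follow-up until death and two point away from it. The two that deal specifically with Phase II or with survival agree with each other.

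**2. Deaths lost if the alternative-therapy bullet is applied**

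The plan gives no OS power or event target, so there is no figure of its own to reproduce. The inputs below are assumptions that are not in the documents:

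- a fraction p = 0.30 to 0.60 of progressed patients start another therapy;
- it starts 0.5 months after they leave protocol therapy;
- post-progression survival is exponential with median m = 3 or 5 months;
- a fraction x = 0.50 to 0.90 of control patients cross over, with an exponential second PFS of median 2 months, independent of survival;
- every patient progresses before death, and there is no administrative cut-off.

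A death is lost if the patient is alive when the new therapy starts.

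- Combination arm: lost = p × 2^(−0.5/m)
- Control arm: lost = p × 2^(−0.5/m) × [(1 − x) + x × m/(m + 2)]

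The term m/(m + 2) is the chance that second progression comes before death when the medians are 2 and m.

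| | Lowest | Highest |
|---|---|---|
| Combination | 0.30 × 0.891 = 27% (m = 3) | 0.60 × 0.933 = 56% (m = 5) |
| Control | 0.267 × (0.10 + 0.90 × 0.60) = 17% (m = 3, x = 0.90) | 0.560 × (0.50 + 0.50 × 0.714) = 48% (m = 5, x = 0.50) |

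The bracketed factor is the ratio of control to combination loss. It runs from 0.64 to 0.86. With median PFS of 3 months in both arms and identical true OS, the resulting gap in Kaplan-Meier median OS is about 0.1-0.4 months at p = 0.30 and 0.5-1.4 months at p = 0.60.

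**3. Effect on the log-rank test**

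From the documents: 40 patients per arm, 4 per month (80/4 = 20 months of accrual), 12 months of further follow-up, median PFS 3 months (stated for TMZ alone and applied to both arms), and the background OS medians of 25 weeks (5.75 months, glioblastoma) and 13.6 months (anaplastic astrocytoma).

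Assumed: identical true OS, 10% of PFS events are deaths, a 1-month lag to new therapy, 30-80% uptake, 50-90% crossover, and a 2-month median second PFS. There were 2,000 simulated trials per setting, tested two-sided at 5%.

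| Median OS | Setting | Deaths observed, control vs combination | Log-rank rejection |
|---|---|---|---|
| 5.75 months | Followed as in 3.6 | 97% vs 97% | 5% |
| 5.75 months | 30% uptake, 50% crossover | 83% vs 78% | 5% |
| 5.75 months | 80% uptake, 90% crossover | 70% vs 48% | 13% |
| 13.6 months | Followed as in 3.6 | 69% vs 69% | 5% |
| 13.6 months | 30% uptake, 50% crossover | 55% vs 53% | 5% |
| 13.6 months | 80% uptake, 90% crossover | 36% vs 26% | 6% |

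At median OS 5.75 months and uptake of 30-50%, rejection stays between 5% and 7.5%. The 13% needs 80% uptake, outside the 30-60% range used in step 2. Nearly all of that excess favours the combination.

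**The case against.** The strongest reply is that the plan already intends follow-up to death. Section 3.6 says so, and the only phase-specific bullet in 3.10.3 agrees. On that reading the alternative-therapy bullet serves Phase I and merely lacks a qualifier. I accept this as the likely intent. It does not remove the conflict: the bullet is unrestricted, it stands in the list that staff use to take patients off study, and 3.10.2 reinforces it.

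Three stronger readings are tempting, and the documents do not support them.

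- A reader might infer that the plan censors OS at next-line therapy. It does not. Section 6.3.9 counts death from any cause, and section 10.2 contains no such censoring rule. The loss occurs only if staff follow the generic bullet against 3.6.
- A reader might infer that the loss falls mainly on the combination arm. The imbalance is an inference from control-only crossover, and on the assumptions above the control arm still loses 64-86% as large a share of its deaths.
- A reader might infer that the OS test is seriously biased. In most settings the rejection rate stays close to 5%.

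It is also fair to say that OS is secondary, has no stated power, and is already acknowledged in section 10.2 as open to influence from crossover. That acknowledgement concerns crossover as an effective salvage treatment and does not cover unequal follow-up. Enrolment in the natural history protocol is required (2.1.1.17) and might supply some dates of death, but this plan does not say that it will be used for survival.

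**Conclusion.** The point holds as an inconsistency between 3.10.3 and 3.6, within 3.10.3 itself, and with the closing step of 3.10.2. Follow-up to death in Phase II appears to be intended but is not secured by the wording.

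If the unrestricted bullet is applied, deaths are lost in both arms in every setting examined, with somewhat more lost in the combination arm. The sizes (27-56% against 17-48%, and a log-rank effect from negligible to modest) are illustrations. They depend on assumed uptake of next-line therapy, timing, post-progression survival and crossover. Certainty attaches to the textual conflict; the by-arm distortion is possible and depends on conduct. Primary PFS could be touched only where a new therapy starts before progression. The point is worth correcting because survival data that are not collected may not be recoverable later.

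**What to change.** - In 3.10.3, limit the alternative-therapy bullet to Phase I, or reword it as a reason to leave treatment and not the study. If it is limited to Phase I, say in 3.6 that the new-therapy clause concerns Phase II, because that clause carries no clear phase limit either.
- In 3.10.2, change the closing step of the 30-day visit so that Phase II patients pass into survival follow-up.
- In 3.6 or section 10.2, state that Phase II patients remain in survival follow-up after any new therapy until death, withdrawal of consent or study end, and that OS is not censored at next-line therapy.

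The cost is a few lines of text in an amendment. The survival contacts are already planned in 3.6, so no new visits or procedures are needed.

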4 CONCOMITANT MEDICATIONS/MEASURES

4.1 MEDICATIONS TO AVOID OR USE WITH PRECAUTION (ZOTIRACICLIB [TG02])

4.1.1 Medications that Prolong QTc

Use of certain medications that prolong QTc interval should be avoided throughout the trial. These medications include but are not limited to: azithromycin, clarithromycin, erythromycin, roxithromycin, metronidazole (with alcohol), moxifloxacin, fluconazole (in cirrhosis), ketoconazole, nelfinavir, chloroquine, mefloquine, halothane, disopyramide, procainamide, quinidine, amiodarone, sotalol, amitriptyline, clomipramine, impipramine, dothiepin, doxepin, risperidone, fluphenazine, haloperidol, clozapine, thioridazine, ziprasidone, pimozide, droperidol, terfenadine, astemizole, probucol, dolasetron mesylate, and cisapride.

However, it is understood that patients with malignancy treated with potentially myelotoxic cytotoxic chemotherapy may require certain classes of medications such as azole antifungal agents and certain antibiotics that have been reported to prolong QTc. If patients require these medications every effort should be made to maintain a normal electrolyte balance with special attention to K⁺ and Mg⁺⁺ levels. An ECG in triplicate should be obtained after beginning such a medication to determine any change to the QTc duration based on the average QTc of triplicate ECGs.

In the event of QT/QTc prolongation, electrolytes will be corrected to keep the potassium and magnesium within normal limits and the ECG in triplicate will be repeated. Patients may be monitored on telemetry at the Investigator's discretion.

During the trial, patients who show a QTc interval prolongation as per CTCAE (based on the average QTc of triplicate ECGs) as calculated by Fridericia's correction formula, should be tested for the electrolytes noted above. If the electrolytes are at normal levels but QTc interval remains prolonged, study drug should be held until QTc interval is no longer prolonged.

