3.1.3 Definition of dose limiting toxicities (DLT)

All patients in the MTD finding phase of the phase I part will be evaluable for assessment of toxicity to define DLTs. The DLT-defining period is the first 4 weeks' treatment in the Phase I study.

Toxicities will be graded per the Common Terminology Criteria for Adverse events (CTCAE) Version 4.0. If multiple toxicities are seen, the presence of DLT should be based on the most severe toxicity experienced. DLT is defined as any of the following events occurring in the first cycle of treatment (4 weeks) and attributable to the study drugs:

- Any of the following hematological toxicities:
 - Grade 4 neutropenia lasting 5 days or more.
 - Febrile neutropenia defined as grade 3-4 neutropenia with fever $\geq 38.5^{\circ}\text{C}$ and/or infection requiring antibiotic or antifungal treatment.
 - Grade 4 thrombocytopenia lasting more than 2 days.
 - Grade 3 thrombocytopenia with bleeding of any duration

- Grade 3 or 4 anemia lasting more than 2 days.
- Any non-hematologic grade 3 or 4 toxicity, except the following
 - nausea or vomiting that responds to symptomatic therapy and lasts ≤ 7 days.
 - Diarrhea that responds to symptomatic therapy within 2 days.
 - fatigue that responds to symptomatic therapy and lasts ≤ 7 days.
 - weight gain (in patients on steroids)
 - venous thromboembolic disease (rationale for not including this event as a DLT described below)
- If there is a dose reduction of either or both study medications or if a dose is held or discontinued in cycle 1, this constitutes a DLT, per PI discretion.
- Grade 4 lymphopenia is not considered as a DLT for this study. All patients for this study have treated with alkylating agents and radiation treatment. Lymphopenia can be highly associated with the previous treatment or have a low threshold to have severe lymphopenia because of the previous treatments. In case of isolated laboratory abnormalities that may not reach clinical significance, a determination will be made by PI or in consultation with the IRB on a case-by-case basis to determine if DLT needs to be declared.
- Failure to recover from treatment related toxicities to be eligible for re-treatment within 4 weeks of the last dose of the drugs.

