3.3.2 Zotiraciclib (TG02) Dose Modifications

If multiple AEs are seen, the dose administered should be based on the dose reduction required for the most severe grade of any single AE. Prior studies of Zotiraciclib (TG02) indicate that non-hematologic toxicities have been the dose-limiting toxicities. Therefore, in the combination regimens, attribution of treatment-related toxicities will be made based on best available information. As Zotiraciclib (TG02) has not been reported with high rates of prolonged myelotoxicity, these toxicities will likely be attributed to temozolomide and dose modifications

made as outlined in Section 3.3.1 above. Conversely, non-hematologic adverse events such as nausea and vomiting, intractable diarrhea, fatigue and prolongation of the QTc interval on ECG will be attributed to Zotiraciclib (TG02). Liver toxicities are a known toxicity of TMZ, which has been tested extensively in patients with high grade glioma. Zotiraciclib (TG02) has also been reported to cause elevated liver enzymes. To better understand the attribution of this toxicity, in the event of elevated ALT/ AST of grade 2 or above when a patient has received the combined treatment, dose modification will be made on one drug at a time. Should the need for dose modification arise again due to the same toxicity, dose of the second drug will be reduced. If a dose reduction occurs in the middle of the cycle, the reduced dose should be applied as soon as the treatment resumes.

Details for dose modification, delay at beginning of each cycle and during the cycle are summarized in Table 8 and Table 11 respectively.

The dose of Zotiraciclib (TG02) will be initiated at the phase I dose for patients enrolled on the dose-finding component or at the MTD for both the cohort expansion of the phase I and the phase II component of the trial. The same dose will be continued unless \geq grade 3 drug related toxicity occurs; treatment will be held until toxicity resolves to grade 1 or less. At that time, the dose will be reduced to one level below the dose that caused the grade 3 toxicity. Only two dose reductions will be allowed for Zotiraciclib (TG02). Patients enrolled prior to determination of the MTD will have stepwise reductions as necessary based on the Table 10 below. Please note, if the MTD is 150 mg/day, then no dose reduction will be allowed. Additionally, if the patient is treated at dose Level 0, only one dose reduction (to 150 mg/day) will be allowed.

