Table 10: Zotiraciclib (TG 02) Dose Modification Table	
Dose Level	TG 02 (mg/day on days 1, 12, 15, 26 per 28 day cycle)*
-1	150
0	200
1	250
2	300

Summary of Dose Modification or Discontinuation

Table 11: Dose Modifications and Delay*				
	Zotiraciclib (TG02)		TMZ	
Grade	Hematologic**	Non-hematologic	Hematologic**	Non-hematologic
0-1	No dose modification	No dose modification	No dose modification	No dose modification

Table 11: Dose Modifications and Delay*				
	Zotiraciclib (TG02)		TMZ	
2	Hold until resolved to ≤ G1; if persists beyond 4 weeks, dose reduce one level.	Hold until resolved to ≤ grade 1; if > 4 weeks then dose reduce 1 level.	Hold until resolved to ≤ grade 1; if > 4 weeks then dose reduce 1 level.	No dose modifications for non-hematologic AEs (G 0-2), unless the adverse event attributed to Temozolomide.
3	If not recovered to ≤ G2 within 3 days, STOP. If recovered to ≤ G2 within 3 days, re-start @ one dose level lower once recovered to G1 or less.***	Delay up to 4 weeks until ≤ Grade 1. If unresolved after 4 weeks, then stop. If resolved to ≤ grade 1; then dose reduce by 1 level.	Hold until resolved to ≤ grade 1; if > 4 weeks, then stop.	Hold until resolved to ≤ grade 2; if greater than 4 weeks then stop. If less than 4 weeks, reduce by one dose level. If the same non-hematologic grade 3 AE recurs after reduction for that AE, then stop.
4	If not recovered to ≤ G2 within 3 days, STOP. If recovered to ≤ G2 within 3 days, re-start @ one dose level lower once recovered to G1 or less	Stop treatment.	Stop treatment.	Stop treatment.

* If the patient develops a lower extremity deep venous thrombosis and requires anticoagulation or intervention (grade 2 or 3 toxicity), treatment may be restarted after a 2-week rest period if the patient is stably anticoagulated and is judged medically stable to begin chemotherapy. (Please note: DVT is graded in the CTC version 4.0 as grade 1= superficial thrombosis, grade 2= DVT, medical intervention indicated, grade 3= uncomplicated pulmonary embolism, medical intervention indicated, grade 4=life-threatening pulmonary embolism, cerebrovascular event, arterial insufficiency, urgent intervention indicated).

** With the exception of lymphopenia, grade 1-4.

***If G3 neutropenia recovers within 72 hours, the Principal Investigator may consider no dose reduction of Zotiraciclib (TG02).

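### For QTc prolongation, section 4.1.1 and Table 11 conflict at grades 1 and 2, and at grades 3 and 4 it is unclear whether the Table 8 and 11 reduction and stop rules also apply

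*Combined protocol and SAP*

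**What the plan says.** Section 4.1.1 sits under the heading on medications to avoid with TG02, but its last paragraph is not limited to patients taking such medications. It covers "patients who show a QTc interval prolongation as per CTCAE", based on averaged triplicate ECGs with Fridericia's correction, and asks for electrolytes to be tested. "If the electrolytes are at normal levels but QTc interval remains prolonged", then "study drug should be held until QTc interval is no longer prolonged". The section states no grade, dose reduction, time limit or permanent stop.

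Section 3.3.2 lists QTc prolongation among the non-hematologic events to be attributed to TG02, and sends the reader to Tables 8 and 11 for details. The TG02 non-hematologic column of Table 11 reads as follows.

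- Grade 0-1: "No dose modification".
- Grade 2: "Hold until resolved to ≤ grade 1; if > 4 weeks then dose reduce 1 level".
- Grade 3: delay for up to 4 weeks, then "If unresolved after 4 weeks, then stop. If resolved to ≤ grade 1; then dose reduce by 1 level".
- Grade 4: stop.

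Table 8 applies the same pattern at the start of each cycle. Section 4.1.1 and these tables do not refer to each other, and no rule of precedence is given.

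Section 3.1.3 defines DLTs. Of cycle 1 holds it says that "if a dose is held or discontinued in cycle 1, this constitutes a DLT, per PI discretion". Section 3.10.1 removes patients from protocol therapy when treatment-related events do not resolve within a 4-week rest period.

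**The concern.** QTc is a named risk of this drug. Section 1.2.2.2 reports hERG inhibition and calls it a risk factor for torsade de pointes. The clinical reassurance there covers doses of 10 to 200 mg. Section 10.1 gives 250 mg as the MTD and keeps it as a possible Phase II dose.

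If two passages give different instructions for the same ECG, two investigators can both follow the protocol and treat the patient differently. That affects exposure and time on treatment. It also affects adverse event data in the post-interim cohort, where toxicity is still the primary endpoint, and possibly the DLT count used for Phase II monitoring.

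**Working it through.** No sample size or power figure is involved in the conflict itself, so the check is a comparison of texts, followed by a short check of the DLT rule.

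**Step 1. Both rules apply to the same event.** Section 4.1.1 is triggered by any CTCAE prolongation. Section 3.3.2 places QTc prolongation with TG02, and hence in the TG02 non-hematologic column. I read the singular study drug in 4.1.1 as TG02, because the heading of 4.1 names it.

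**Step 2. Side by side, with normal electrolytes.**

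| Grade | 4.1.1 | Table 11, TG02 non-hematologic | Result |
|---|---|---|---|
| 1 | Hold until not prolonged | No modification | Direct conflict |
| 2 | Hold until not prolonged | Hold to grade 1 or less; reduce one level if over 4 weeks | Same first step, different resume point |
| 3 | Hold until not prolonged; silent on what follows | Hold to grade 1 or less, then reduce one level; stop if unresolved after 4 weeks | Same first step; unclear whether reduction and stop also apply |
| 4 | Hold until not prolonged; silent on stopping | Stop | Unclear whether the stop also applies |

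With abnormal electrolytes, 4.1.1 first corrects them and repeats the ECG, whereas Table 11 holds from grade 2.

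**Step 3. The resume point is not defined.** The only numeric QTc limits in the documents are the eligibility limits in 2.1.2.8 (above 450 ms for men, above 470 ms for women). Section 4.1.1 relies on CTCAE, whose thresholds are not reproduced. Whether no longer prolonged means below the CTCAE grade 1 threshold or within the eligibility limits cannot be settled from the text.

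**Step 4. Consequence under 3.10.1.** Take a grade 1 prolongation with normal electrolytes that does not go away. Under 4.1.1 the drug is held, and after 4 weeks 3.10.1 can end protocol therapy. Under Table 11 there is no hold, hence no rest period, and treatment continues at the same dose.

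**Step 5. DLT status under 3.1.3.**

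- Grades 3-4: an attributable non-hematologic event is a DLT under either passage, and QTc is not among the listed exceptions.
- Grade 2, normal electrolytes: both passages hold, so both reach the same PI-discretion clause.
- Grade 2, abnormal electrolytes: Table 11 holds, while 4.1.1 corrects first.
- Grade 1, normal electrolytes: 4.1.1 holds (a possible DLT), while Table 11 does not.

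So the passage read changes whether a hold occurs, mainly in the last two cases. A smaller route is the 3.1.3 criterion on failure to recover for re-treatment within 4 weeks, because the two passages set different recovery points.

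**Step 6. The Phase II toxicity rule.** Section 10.2 stops an arm if Pr(DLT rate > 0.35 | data) > 0.9 with a Beta(0.1, 0.4) prior. With r DLTs in n patients the posterior is Beta(0.1 + r, 0.4 + n − r). The stated boundaries are reproduced:

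| n | Boundary r | Pr at r | Pr at r − 1 | r/n |
|---|---|---|---|---|
| 5 | 4 | 0.975 | 0.844 | 80% |
| 10 | 6 | 0.936 | 0.809 | 60% |
| 20 | 10 | 0.904 | 0.802 | 50% |
| 30 | 15 | 0.948 | 0.895 | 50% |

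One reclassified patient changes the decision only when an arm is already one DLT short of its boundary. That is true of any event type.

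**The case against.** The strongest reply is that the texts can be read together. Section 4.1.1 adds an electrolyte check and a hold, and the dose-modification section supplies reduction and stopping. On that reading, silence in 4.1.1 at grades 3-4 is not permission to resume unchanged, and 3.10.1 supplies the 4-week limit that 4.1.1 lacks. This largely stands for grades 3-4. What remains there is a missing cross-reference.

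It does not resolve grades 1 and 2. A hold and no modification cannot both be followed, and Table 11's title covers delay as well as modification, so its grade 0-1 row cannot be read as leaving holds open. Saying that the specific section governs does not help either. The protocol states no such rule, and if 4.1.1 displaced the tables, the grade 3 reduction and grade 4 stop would go with them. Nor does the protocol say that the stricter text applies.

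The second reply is that few patients will be affected, and this too has force. Section 1.2.2.2 reports no clinically meaningful QTc change in 73 patients at 10 to 200 mg, a range that includes the post-interim dose of 200 mg but not 250 mg. Cycle 1 has one scheduled on-treatment ECG, in week 4, so of the cycle 1 TG02 doses (days -3, 1, 12, 15 and 26) usually only day 26 could be held because of it. Unscheduled ECGs under 4.1.1 remain possible.

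**Conclusion.** The conflict is real but narrow. The instructions clash outright at grade 1 with normal electrolytes, and in the resume point at grade 2. At grades 3-4 there is a gap: the text does not say whether the Table 8 and 11 reduction and stop rules operate alongside 4.1.1. The most concrete consequence is that a persistent grade 1 prolongation could end protocol therapy under one passage and not under the other.

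A reader might infer three stronger things, and the documents support none of them.

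- That the passages prescribe opposite actions at every grade. With normal electrolytes, both begin with a hold at grades 2 and 3.
- That 4.1.1 allows treatment to resume after a grade 4 event. It does not address stopping, and the tables do.
- That the choice of passage decides DLT status or a Phase II stop. Section 3.1.3 sets DLT status, at PI discretion for holds, and grades 3-4 are DLTs either way. The documents give no QTc event rate, so an effect on the boundaries cannot be sized.

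The conclusion assumes that study drug in 4.1.1 means TG02. Any Phase II effect further assumes that the hold clause of 3.1.3, whose DLT period is set for Phase I, carries over to 10.2. MTD finding is already complete (10.1), so the exposure now lies in the 12-patient post-interim cohort and in Phase II.

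**What to change.** Reconcile 4.1.1, 3.3.2, Table 8, Table 11 and 3.10.1 for QTc prolongation, grade by grade, covering both normal and abnormal electrolytes. Cross-reference the agreed text in each place. Define when QTc counts as no longer prolonged, including whether CTCAE or the eligibility limits apply. State how a QTc hold in cycle 1 is treated under 3.1.3, and whether that also applies to Phase II toxicity monitoring. Which action applies at each grade is a clinical decision for the sponsor. The cost is amendment wording only: no change to sample size, visits or analysis.
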